Physical examination, neurological examination, ECGs, vital signs and questionnaires: Physical examination, neurological examinations, ECGs, vital signs and questionnaires (C-SSRS, Bond and Lader VAS) recorded during the study will be individually listed and quantitative parameters will be summarised by using descriptive statistics. For vital signs and ECG parameters, all values recorded during the study will be individually listed and flagged for abnormalities and for clinical significance (assessed by investigator). In addition, values and abnormalities (not clinically significant and clinically significant) will be described by dose group and overall, at screening, study baseline (D-1, or D1 predose), each evaluation under treatment phase and at the end of the study. Change between the value at baseline and the value at each evaluation under treatment phase and at end of study visit will be described for each parameter by dose group and overall.

Laboratory parameters: All laboratory values recorded during the study will be individually listed and flagged for values outside reference ranges and for clinical significance (assessed by investigator). Quantitative parameters will be summarized by descriptive statistics. Values, position according to laboratory range and clinical significance assessment will be described at screening, D-1 (baseline) and at D2, D4 and D6 (only for the cohorts 160 mg, 260 mg, 380 mg and 500 mg) by dose group and overall. Change between the value at baseline and the value at post-dose visits will be described for each parameter by dose group and overall. All quantitative and qualitative urinary test results will be listed, sorted dose group, visit and subject.

Pharmacokinetic parameters:

Plasma concentrations will be summarized by dose level and time point. The derived PK parameters will be listed by subject and summarized by dose level.

In addition, the hypothesis that AUC and C_{max} are dose proportional will be formally tested using a power model approach.

Pharmacodynamic parameters:

ECG parameters will be summarized by dose level and time points on actual values and changes from baseline.

Placebo corrected changes from baseline ($\Delta\Delta$) will be calculated with their 90% CI for each dose level and time points and displayed.

Subjects meeting predefined criteria for ECG parameters abnormality and results of the morphological analysis will be summarized by dose level using count and percentage.

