An optional post hoc concentration-response analysis between $\Delta QTCF$ and DNDI-6148 concentrations will be performed on ECG data issued from Holter extraction. $\Delta\Delta QTCF$ with their 90% CI will be estimated from the model at each dose C_{max} geometric means.

Table 1 Study Flow Chart

Visit/Period	Screening	Inclusion		Treatmer	nt period		Ambula	tory visits
Day	D-28 to D-2	D-1	D1	D2	D3	D4	D5 ⁴	D6 ⁴
Informed consent	Х							
Eligibility criteria	Х	X ²	X ²					
Previous Medical / Surgical History	Χ	X ²						
Prior/concomitant medications	Х	Χ	Х	Х	Х	Х	Х	Х
Physical examination	Х	Х	Х	Х		Χ		Х
Clinical neurological exam	Х	Х	X ³			Х		Х
Body weight	Х					Х		Х
Hematology	Х	Х		Х		Χ		Х
Hemostasis	Х	Х		Х		Χ		Х
Hormonology	Х	Х				Χ		Х
Biochemistry	Χ	Х		Х		Χ		Х
Urinalysis	Х	X		Х		Х		Х
Serology	Χ							
Diagnostic test of SARS-CoV-2		Χ						
Urine drug screen	Х	Χ						
Alcohol breath test	Х	Χ						
Admission		Χ						
Discharge						Χ		
Randomization			X					
Study Drug Administration			X					
Meals		Χ	Х	Х	Х	Χ		
Blood pressure / Heart rate / Body temperature	Х	Χ	Х	Х	Х	Χ	Х	Х
CSSR-S evaluation – Bond & Lader questionnaire	Х	Х	X ³			Х		Х
12-lead ECG recording	Х	Х	Х	Х	Х	Χ	Х	Х
Holter 24-hours recording			←	\longrightarrow				
Blood sample for Pharmacokinetics ¹			X	X	Х	Х	Х	Х
Urine collection for Pharmacokinetics ¹			Х	Х	Х	Х		
AE and pre-dose events collection						_		\rightarrow

1 See Detail on details Study Flow Chart

2Recheck only

3 Only around T6h

4 only for the cohorts 160 mg, 260 mg, 380 mg and 500 mg

Visit/Period	Treatment period							Ambulat	ory visits									
Day							D1							D2	D3	D4	D5 ³	D6 ³
Theoritical time	Predose	T0h	T30min	T1h	T1h30	T2h	T2h30	T3h	T4h	T5h	T6h	T9h	T12h	T24h	T48h	T72h	T96h	T120h
Prior/concomitant	\leftarrow												•			•		 →
medications	/																	
Physical examination	Х													Х		Х		Х
Clinical Neurological exam											Χ					Х		Х
Body weight																Х		Х
Hematology														Х		Х		Х
Hemostasis														Х		Х		Х
Hormonology																Х		Χ
Biochemistry														Х		Х		Х
Urinalysis														Х		Х		Х
Discharge																Х		
Randomization		Χ																
Study Drug																		
Administration		Χ																
Meals									Χ				Х	Х	Х	Х		
Blood pressure / Heart																		
rate /body temperature	Χ			Х	X ²	Χ	Х	Χ	Χ	X ³	Х		Х	Х	Х	Х	Х	X
CSSR-S evaluation – Bond & Lader questionnaire											Х					X		Х
12-lead ECG recording	X ¹			Х		Х		Х	. V			Х	V	V	Х	X	Х	

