- QT/QTc interval > 500 ms

and for maximum changes from baseline:

- ΔQTc interval > 30 ms
- ΔQTc interval > 60 ms

All parameters and their changes from baseline will be summarized by dose regimen and time-point (including Δ HR, Δ RR, Δ PR, Δ QRS, Δ QT). Placebo group extracts will be used for the double-delta analysis of QT.

QT interval calculation would be manually checked by a cardiologist.

A concentration-response analysis between $\Delta QTcF$ and DNDI-6148 concentrations will be performed on ECG data issued from Holter extraction. $\Delta\Delta QTcF$ with their 90% CI will be estimated from the model at each dose Cmax geometric means.

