Categorical analysis consisting in counts and percentages of abnormal values per dose level will be performed for HR, QTc, PR and QRS according to regulatory thresholds for raw data and changes from baseline.

Treatment emergent morphological findings will be summarized as counts and percentage of subjects presenting at least one finding by dose level.

Concentration-response relationship will be investigated between change from baseline in QTcF and DNDI-6148 concentrations. First, graphics of change from baseline in QTcF and concentrations of DNDI-6148 will be generated in order to visualize the overall pattern of each relationship. Modelling of each of these graphics will then be performed by means of linear or nonlinear mixed model.

For each compound, a model will be selected according to the overall precision of the model towards observed data and diagnostic plots. Using these models, predictions of changes from baseline at concentrations of interest (e.g. Cmax) will be obtained from the concentration-response models with their 90%CI.

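### Section 11.1.3 reports change from baseline in QTcF from the concentration-response model, where the Synopsis and Section 7 report the placebo-corrected change; it also chooses the model by fit to the same data

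*Protocol*

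**What the plan says.** Three places in the protocol describe one model.

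- **Section 11.1.3 (Pharmacodynamic).** "Concentration-response relationship will be investigated between change from baseline in QTcF and DNDI-6148 concentrations". After the data have been graphed, "Modelling of each of these graphics will then be performed by means of linear or nonlinear mixed model". The choice is made thus: "a model will be selected according to the overall precision of the model towards observed data and diagnostic plots". The output is "predictions of changes from baseline at concentrations of interest (e.g. Cmax) will be obtained from the concentration-response models with their 90%CI". Neither placebo nor a time effect is mentioned.
- **Section 7.** The response is again ΔQTcF, but the output is ΔΔQTcF, "with their 90% CI will be estimated from the model at each dose Cmax geometric means". The same section says "Placebo group extracts will be used for the double-delta analysis of QT". It states without qualification that the concentration-response analysis will be done, once the Holter data are analysed.
- **Synopsis (Statistics).** The output is ΔΔQTcF, as in Section 7, but the analysis is introduced as "An optional post hoc concentration-response analysis between" ΔQTcF and concentration. The Synopsis also plans "Placebo corrected changes from baseline" with 90% CI by dose level and time point. Section 11.1.3 does not repeat that.

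Baseline is the average of three pre-dose triplicates on Day 1 (Section 7). Dosing is at about 8 a.m. (Section 5.1.3) and lunch is at 4 h (Section 8.2.3).

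**The concern.** A 90% CI for ΔQTcF at Cmax and a 90% CI for ΔΔQTcF at Cmax answer different questions. An analyst could follow either text and claim to have kept to the protocol. Only the placebo-corrected quantity isolates the drug in this design: every subject is dosed at about the same clock time, so high concentrations recur at about the same time of day, and a pre-dose baseline does not remove what happens to QTcF afterwards without drug.

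The selection rule is a second, independent matter. An interval computed as if the chosen model had been fixed in advance takes no account of the choice.

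What is at stake is the only model-based cardiac estimate the protocol describes. One of the two options in Section 7 is to analyse the Holter data after the multiple-dose study, so that both data sets can be pooled.

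**Working it through.** **The plan's own figures.** None exists for this analysis: Section 11.2 says no formal sample size calculation was made, and no QTc standard deviation, margin or drift is given. Only the counts can be checked: 8 × (6 + 2) = 64 subjects, of whom 8 × 6 = 48 are on active drug and 8 × 2 = 16 on placebo.

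**The two quantities.** Let d(t) be the mean QTcF change from the pre-dose baseline at time t without drug, and e(c) the drug effect at concentration c.

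- Active subject: mean ΔQTcF(t) = d(t) + e(c).
- Placebo subject: mean ΔQTcF(t) = d(t).
- Section 11.1.3 quantity at Cmax: d(tmax) + e(Cmax).
- Synopsis and Section 7 quantity: e(Cmax).

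They agree only if d(tmax) = 0. The baseline is taken at 60, 40 and 20 minutes before dosing, so it cannot make d(t) zero at later times.

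**Illustration of size.** 600 simulated trials per scenario, with true drug effect zero.

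- From the protocol: 48 active and 16 placebo subjects, the eight planned doses, ten post-dose times from 0.5 to 24 h common to all cohorts, and half-life 11 h (predicted) or 20 h (observed in the first cohorts).
- Assumed: between-subject SD 5 ms, within-subject SD 6 ms, absorption rate 1.5 per hour, 25% between-subject variability in exposure, and the drift shapes and sizes.
- Uncorrected model: ΔQTcF on concentration with a random intercept, predicting ΔQTcF at the 500 mg geometric mean Cmax. Fitted to active subjects alone and to all subjects, with almost identical results.
- Corrected model: adds treatment and nominal time for all subjects, and predicts ΔΔQTcF.
- Each 90% CI is the estimate ± 1.645 × SE. Coverage is of the true drug effect, zero.

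| Assumed drift | Error of uncorrected prediction (ms) | Coverage of its 90% CI |
|---|---|---|
| None | about 0 | 0.88 to 0.91 |
| Peak near 3 h: 3 ms | +3.4 to +4.1 | 0.13 to 0.30 |
| Peak near 3 h: 5 ms | +5.7 to +6.8 | 0.00 to 0.02 |
| Peak near 3 h: 8 ms | +9.0 to +10.9 | 0.00 |
| Dip near 6 h: 3 ms | -1.3 to -1.5 | 0.74 to 0.78 |
| Dip near 6 h: 5 ms | -2.3 to -2.5 | 0.48 to 0.54 |
| Dip near 6 h: 8 ms | -3.7 to -4.1 | 0.14 to 0.22 |
| Peak near 12 h: 3 to 8 ms | -0.2 to +1.1 | 0.82 to 0.91 |

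Across all scenarios the corrected model had error -0.1 to +0.2 ms and coverage 0.87 to 0.92. Its mean SE was about 2.1 ms against 1.5 ms, so the 90% half-width is 1.645 × 2.1 = 3.5 ms against 1.645 × 1.5 = 2.5 ms.

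**Selection.** Section 11.1.3 gives a model family and a fit-based choice, with no primary model and no numeric criterion. Its effect on the interval was not simulated, and no figure is claimed.

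**The case against.** The strongest reply is that Section 11.1.3 is only looser wording for the same output. All three places model ΔQTcF, one model can yield both quantities, and the Synopsis itself uses the phrase change from baseline for the placebo-corrected value. Section 7 says placebo extracts serve the double-delta, and the by-time-point placebo-corrected analysis in the Synopsis would expose drift. Treatment, time and baseline terms are normally settled in the analysis plan, which is not shown. The analysis is exploratory, conditional on the Holter data being analysed, and reported separately. Dose escalation uses centrally read safety ECGs, and no decision rule hangs on this interval. Looking at plots before choosing a form is ordinary in exploratory work.

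Much of this stands. A reader might infer that 11.1.3 prescribes a model of active subjects only, with no time term. It does not: it leaves those terms unspecified, and their absence from a protocol is no fault. The uncorrected rows of the table therefore show what can happen, not what the plan dictates.

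Two things remain. The quantity named in 11.1.3 is not the one named elsewhere, and ΔQTcF contains d(t) however well the model is built. The selection rule is a stated rule, not an omission.

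**Conclusion.** The point holds as a minor inconsistency in an exploratory analysis. Section 11.1.3 must be reconciled with the Synopsis and Section 7 on the quantity reported. The drift carried by a ΔQTcF prediction can go in either direction, and its size depends on drift timing relative to tmax, which the documents do not give.

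Three stronger readings are not supported:

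- **That an error of 5 to 8 ms or more should be expected.** It arises only when an assumed drift of that order peaks near tmax. It is about half the drift for a dip near 6 h and close to zero for a peak near 12 h. The table also refers to 500 mg, where Table 5 predicts a Cmax of 18,105 ng/mL, about 2.5 times (18,105 / 7,300) the 7.3 µg/mL escalation limit in Section 3.5.3, so that dose may not be reached under the present rules.
- **That choosing the model from the data causes the drift.** It does not. Drift comes from the lack of placebo correction in the reported quantity; selection bears on whether the nominal 90% CI is honest.
- **That the interval is too narrow by a known amount.** This was not quantified.

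**What to change.** 1. In Section 11.1.3, replace the predicted change from baseline by ΔΔQTcF with 90% CI at each dose's geometric mean Cmax, as in the Synopsis and Section 7.
2. Describe the status of the analysis in one way: the Synopsis calls it optional and post hoc, while Section 7 says it will be done once Holter data are analysed.
3. Name one primary model before the data are seen: a linear mixed model of ΔQTcF on concentration (zero for placebo), treatment indicator, nominal time and baseline QTcF, with all placebo subjects included. Allow nonlinear forms only under a stated lack-of-fit criterion. The detail can sit in the analysis plan if 11.1.3 refers to it instead of the present selection rule.

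The cost is wording; no new data are needed. The statistical price is a somewhat larger standard error, about 2.1 against 1.5 ms under the assumptions above.

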11.2. Sample size

No formal calculation was performed. It has been decided to include 8 subjects (6 active and 2 placebo) within each treatment group, which, given the exploratory nature of the trial, is considered as a sufficient number of subjects.

11.3. Level of significance to be used

The level of significance will be fixed at 0.05.

Tests will be two-tailed with no multiplicity adjustment.

11.4. Interim Analysis

Interim PK calculations will be performed at the end of each dose group based on blinded data.

11.5. Procedure for accounting, for missing, unused, and spurious data

Missing data values will not be replaced. Reason for missing data should be provided.

11.6. Procedures for reporting any deviation(s) from original statistical plan

This plan may be revised during the study to accommodate protocol amendments and to make changes to adapt to unexpected issues in study execution and data collection that could affect planned analyses. These revisions will be based on review of the data, and a final plan will be issued prior to database lock, if applicable.

11.7. Selection of subjects to be included in the analyses

In case of incorrect treatment assigned, subjects will be analysed in the treatment group they actually were included and the treatment they received.

12. QUALITY CONTROL AND ASSURANCE

12.1. Quality Assurance

The study will be carried out in conformity with legal conditions and French regulations, and with respect to GCP (ICH E6 (R2)) guideline. The Quality Assurance system in force at EUROFINS OPTIMED will apply, except for any specific clauses added to the protocol or specified in writing by the Sponsor before the start of the study.

12.2. Quality Control

The main study stages (coherence between source and CRF for: eligibility criteria, main evaluation criteria, AEs) will be submitted to a quality control process.

12.3. Sponsor audits and inspections by regulatory agencies

The study may be subjected to on-site audit visit by the Sponsor and inspection by applicable Regulatory Authorities to verify that the study is conducted in compliance with the principles of GCP and with the study protocol. The auditor/inspectors will have direct access to medical records, source documents, and all documents and facilities relevant to the clinical trial.

The Investigator agrees to allow the auditors/inspectors to have direct access to study records for review, being understood that these personnel are bound by professional secrecy, and as such will not disclose any personal identity or personal medical information.

The confidentiality of the data and the anonymity of the subjects should be respected during these inspections.

13. ETHICS

13.1. Informed consent form

The persons participating in the study will be selected during a screening visit. During this meeting, the study objectives and methodology will be explained.

The volunteer subjects will receive a synthesis document explaining the requirements of research, the title and the objectives of the study, the detailed research protocol and the risks and constraints of the research.

Before being included in the study, each participant must give his written consent. The text of the consent is to be signed and dated and initialled on each page by the subject and dated and signed by the Investigator.

13.2. Ethics Committee and Competent Authorities

The study will be carried out in conformity with the principles of the Declaration of Helsinki as modified in Fortaleza (2013), and National Regulation.

This study will be undertaken after approval by the Ethics Committee and of the Competent Authorities.

13.3. Protocol amendments

Any protocol amendment must be approved and signed by the sponsor and the Principal investigator and is to be submitted to the appropriate IEC for information and approval in accordance with local requirements, and to regulatory agencies if required. Approval by IEC (and Regulatory Authority, if applicable) must be awaited before any changes can be implemented, except for changes necessary to eliminate an immediate hazard to trial subjects, or when the change involves only logistical or administrative aspects of the trial.

The protocol amendment can be initiated by either sponsor or by any Principal investigator.

The investigator will provide in writing the reasons for the proposed amendment and will discuss with the medical responsible and the sponsor.

Depending on the importance of the changes to the study conditions, the amendment may be sent to the Ethics Committee and/or Health Competent Authorities either for approval or for information.

13.4. Protocol deviations

The Principal investigator will ensure that the study protocol is strictly adhered to throughout, and that all data are collected and recorded correctly on the CRF.

Any protocol deviations will be notified to the Monitor/Sponsor on an ongoing basis, and no later than the date of the blind review and will give rise to a discussion to define their status (minor – major). Critical deviations should be communicated to the Sponsor on timely manner.

13.5. Access to data by the subjects

In conformity with the law, any subjects who so wish may access any data concerning them, at the end of the research. They should address their request in writing to the Investigator, and will obtain a response within 8 working days.

14. DATA HANDLING AND RECORD KEEPING

14.1. Archival

All documents related to the study must be kept by the Investigator in appropriate files. The archives of the subjects, original informed consent forms, source documents, case report forms, inventory of study products, correspondence with the Sponsor and Ethics committee related to the study, must be filed. The Investigator authorises direct access to the source documents for monitoring, audits and inspections. The Investigator keeps a list identifying the subject names (with addresses and/or medical file numbers), their respective code number and the dates of entry into the study and end of study, in order to be able to verify the concordance between the data contained in the case report forms and those in the source documents.

These documents must be kept on the Investigator site until at least twenty-five years. Even at the end of this period, no destruction can be achieved unless authorized in writing by a duly mandated Sponsor's representative.

If the Investigator/Institution is no longer able to be responsible for essential documents the Sponsor must be notified in writing of this change and informed as to whom the responsibility has been transferred.

14.2. Confidentiality

All information obtained during the study (except the informed consent form data) will be input onto computer by EUROFINS OPTIMED, subcontracted by the Sponsor in conformity with the "Information Technology and Liberty Law" (Article 40 of 6 January 1978) which respects the MR-001 and the European Regulation N°2016/679 on General Data Protection Regulation (GDPR).

14.3. Ownership of results

The Sponsor is the sole owner of the data and research results. He reserves the right to use them in any form whatsoever, to submit them to the Health Authorities of any country.

Should the study generate results likely to be patented, then only the Sponsor will be authorised to depose such a patent, in his name and at his costs.

15. FINANCING AND INSURANCE

The Sponsor certifies that it has taken out a liability insurance policy which covers the current research in accordance with local laws and requirements.

An insurance certificate will be provided to the Investigator and to the CPP.

16. PUBLICATION

All information issuing from the study will be considered to be confidential and must not be divulged without the Sponsor's prior agreement.

The study results may be published or presented by the Investigator or analysis experts, in collaboration with the Sponsor, with the sponsor's written permission. The Sponsor may use the study results for any publication or communication, with the written agreement of the Investigator or the analysis experts if they are cited.

18. LIST OF APPENDICES

APPENDIX I DECLARATION OF HELSINKI

APPENDIX II ANSM GUIDELINE FOR SAE, SAR, SUSAR, NEW FACTS DECLARATION

APPENDIX III ORASWEET® PRODUCT INFORMATION

APPENDIX IV Visual Analog Scale (VAS) Bond and Lader questionnaire

APPENDIX V Columbia-Suicide severity rating scale

APPENDIX I DECLARATION OF HELSINKI

WMA Declaration of Helsinki - Ethical Principles for Medical Research Involving Human Subjects

Adopted by the 18th WMA General Assembly, Helsinki, Finland, June 1964 and amended by the:

29th WMA General Assembly, Tokyo, Japan, October 1975 35th WMA General Assembly, Venice, Italy, October 1983

41st WMA General Assembly, Hong Kong, September 1989

48th WMA General Assembly, Somerset West, Republic of South Africa, October 1996
52nd WMA General Assembly, Edinburgh, Scotland, October 2000
53rd WMA General Assembly, Washington DC, USA, October 2002 (Note of
Clarification added)

55th WMA General Assembly, Tokyo, Japan, October 2004 (Note of Clarification added)
59th WMA General Assembly, Seoul, Republic of Korea, October 2008
64th WMA General Assembly, Fortaleza, Brazil, October 2013

Preamble

 The World Medical Association (WMA) has developed the Declaration of Helsinki as a statement of ethical principles for medical research involving human subjects, including research on identifiable human material and data.

The Declaration is intended to be read as a whole and each of its constituent paragraphs should be applied with consideration of all other relevant paragraphs.

Consistent with the mandate of the WMA, the Declaration is addressed primarily to physicians. The WMA encourages others who are involved in medical research involving human subjects to adopt these principles.

General Principles

The Declaration of Geneva of the WMA binds the physician with the words,

1/8

"The health of my patient will be my first consideration," and the International Code of Medical Ethics declares that, "A physician shall act in the patient's best interest when providing medical care."

- 4. It is the duty of the physician to promote and safeguard the health, well-being and rights of patients, including those who are involved in medical research. The physician's knowledge and conscience are dedicated to the fulfilment of this duty.
- Medical progress is based on research that ultimately must include studies involving human subjects.
- 6. The primary purpose of medical research involving human subjects is to understand the causes, development and effects of diseases and improve preventive, diagnostic and therapeutic interventions (methods, procedures and treatments). Even the best proven interventions must be evaluated continually through research for their safety, effectiveness, efficiency, accessibility and quality.
- Medical research is subject to ethical standards that promote and ensure respect for all human subjects and protect their health and rights.
- While the primary purpose of medical research is to generate new knowledge, this goal can never take precedence over the rights and interests of individual research subjects.
- 9. It is the duty of physicians who are involved in medical research to protect the life, health, dignity, integrity, right to self-determination, privacy, and confidentiality of personal information of research subjects. The responsibility for the protection of research subjects must always rest with the physician or other health care professionals and never with the research subjects, even though they have given consent.
- 10. Physicians must consider the ethical, legal and regulatory norms and standards for research involving human subjects in their own countries as well as applicable international norms and standards. No national or international ethical, legal or regulatory requirement should reduce or eliminate any of the protections for research subjects set forth in this Declaration.
- Medical research should be conducted in a manner that minimises possible harm to the environment.
- 12. Medical research involving human subjects must be conducted only by

individuals with the appropriate ethics and scientific education, training and qualifications. Research on patients or healthy volunteers requires the supervision of a competent and appropriately qualified physician or other health care professional.

- Groups that are underrepresented in medical research should be provided appropriate access to participation in research.
- 14. Physicians who combine medical research with medical care should involve their patients in research only to the extent that this is justified by its potential preventive, diagnostic or therapeutic value and if the physician has good reason to believe that participation in the research study will not adversely affect the health of the patients who serve as research subjects.
- Appropriate compensation and treatment for subjects who are harmed as a result of participating in research must be ensured.

Risks, Burdens and Benefits

 In medical practice and in medical research, most interventions involve risks and burdens.

Medical research involving human subjects may only be conducted if the importance of the objective outweighs the risks and burdens to the research subjects.

17. All medical research involving human subjects must be preceded by careful assessment of predictable risks and burdens to the individuals and groups involved in the research in comparison with foreseeable benefits to them and to other individuals or groups affected by the condition under investigation.

Measures to minimise the risks must be implemented. The risks must be continuously monitored, assessed and documented by the researcher.

18. Physicians may not be involved in a research study involving human subjects unless they are confident that the risks have been adequately assessed and can be satisfactorily managed.

When the risks are found to outweigh the potential benefits or when there is conclusive proof of definitive outcomes, physicians must assess whether to continue, modify or immediately stop the study.

Vulnerable Groups and Individuals

 Some groups and individuals are particularly vulnerable and may have an increased likelihood of being wronged or of incurring additional harm.

All vulnerable groups and individuals should receive specifically considered protection.

20. Medical research with a vulnerable group is only justified if the research is responsive to the health needs or priorities of this group and the research cannot be carried out in a non-vulnerable group. In addition, this group should stand to benefit from the knowledge, practices or interventions that result from the research.

Scientific Requirements and Research Protocols

- 21. Medical research involving human subjects must conform to generally accepted scientific principles, be based on a thorough knowledge of the scientific literature, other relevant sources of information, and adequate laboratory and, as appropriate, animal experimentation. The welfare of animals used for research must be respected.
- 22. The design and performance of each research study involving human subjects must be clearly described and justified in a research protocol.

The protocol should contain a statement of the ethical considerations involved and should indicate how the principles in this Declaration have been addressed. The protocol should include information regarding funding, sponsors, institutional affiliations, potential conflicts of interest, incentives for subjects and information regarding provisions for treating and/or compensating subjects who are harmed as a consequence of participation in the research study.

In clinical trials, the protocol must also describe appropriate arrangements for post-trial provisions.

Research Ethics Committees

23. The research protocol must be submitted for consideration, comment, guidance and approval to the concerned research ethics committee before the study begins. This committee must be transparent in its functioning, must be independent of the researcher, the sponsor and any other undue influence and must be duly qualified. It must take into consideration the laws and regulations of the country or countries in which the research is to be performed as well as applicable international norms and

standards but these must not be allowed to reduce or eliminate any of the protections for research subjects set forth in this Declaration.

The committee must have the right to monitor ongoing studies. The researcher must provide monitoring information to the committee, especially information about any serious adverse events. No amendment to the protocol may be made without consideration and approval by the committee. After the end of the study, the researchers must submit a final report to the committee containing a summary of the study's findings and conclusions.

Privacy and Confidentiality

 Every precaution must be taken to protect the privacy of research subjects and the confidentiality of their personal information.

Informed Consent

- 25. Participation by individuals capable of giving informed consent as subjects in medical research must be voluntary. Although it may be appropriate to consult family members or community leaders, no individual capable of giving informed consent may be enrolled in a research study unless he or she freely agrees.
- 26. In medical research involving human subjects capable of giving informed consent, each potential subject must be adequately informed of the aims, methods, sources of funding, any possible conflicts of interest, institutional affiliations of the researcher, the anticipated benefits and potential risks of the study and the discomfort it may entail, post-study provisions and any other relevant aspects of the study. The potential subject must be informed of the right to refuse to participate in the study or to withdraw consent to participate at any time without reprisal. Special attention should be given to the specific information needs of individual potential subjects as well as to the methods used to deliver the information.

After ensuring that the potential subject has understood the information, the physician or another appropriately qualified individual must then seek the potential subject's freely-given informed consent, preferably in writing. If the consent cannot be expressed in writing, the non-written consent must be formally documented and witnessed.

All medical research subjects should be given the option of being informed about the general outcome and results of the study.

- 27. When seeking informed consent for participation in a research study the physician must be particularly cautious if the potential subject is in a dependent relationship with the physician or may consent under duress. In such situations the informed consent must be sought by an appropriately qualified individual who is completely independent of this relationship.
- 28. For a potential research subject who is incapable of giving informed consent, the physician must seek informed consent from the legally authorised representative. These individuals must not be included in a research study that has no likelihood of benefit for them unless it is intended to promote the health of the group represented by the potential subject, the research cannot instead be performed with persons capable of providing informed consent, and the research entails only minimal risk and minimal burden.
- 29. When a potential research subject who is deemed incapable of giving informed consent is able to give assent to decisions about participation in research, the physician must seek that assent in addition to the consent of the legally authorised representative. The potential subject's dissent should be respected.
- 30. Research involving subjects who are physically or mentally incapable of giving consent, for example, unconscious patients, may be done only if the physical or mental condition that prevents giving informed consent is a necessary characteristic of the research group. In such circumstances the physician must seek informed consent from the legally authorised representative. If no such representative is available and if the research cannot be delayed, the study may proceed without informed consent provided that the specific reasons for involving subjects with a condition that renders them unable to give informed consent have been stated in the research protocol and the study has been approved by a research ethics committee. Consent to remain in the research must be obtained as soon as possible from the subject or a legally authorised representative.
- 31. The physician must fully inform the patient which aspects of their care are related to the research. The refusal of a patient to participate in a study or the patient's decision to withdraw from the study must never adversely affect the patient-physician relationship.
- 32. For medical research using identifiable human material or data, such as research on material or data contained in biobanks or similar repositories, physicians must seek informed consent for its collection, storage and/or reuse. There may be exceptional situations where consent would be impossible or impracticable to obtain

for such research. In such situations the research may be done only after consideration and approval of a research ethics committee.

Use of Placebo

33. The benefits, risks, burdens and effectiveness of a new intervention must be tested against those of the best proven intervention(s), except in the following circumstances:

Where no proven intervention exists, the use of placebo, or no intervention, is acceptable; or

Where for compelling and scientifically sound methodological reasons the use of any intervention less effective than the best proven one, the use of placebo, or no intervention is necessary to determine the efficacy or safety of an intervention

and the patients who receive any intervention less effective than the best proven one, placebo, or no intervention will not be subject to additional risks of serious or irreversible harm as a result of not receiving the best proven intervention.

Extreme care must be taken to avoid abuse of this option.

Post-Trial Provisions

